1. PROTOCOL SUMMARY

1.1. Synopsis

Protocol Title: A Global, Molecular Disease Characterization Initiative (MDCI) in Oncology Clinical trials

Short Title: Molecular Disease Characterization Initiative (MDCI)

Rationale:

It is estimated that over 600,000 people will die from cancer in 2020 [American Cancer Society (ACS), 2020]; advancement is needed in further understanding biological mechanisms underpinning clinical outcomes and identification of novel pathways contributing to oncogenesis or treatment resistance.

The aim of this protocol is to leverage science and data, by comprehensively analyzing and compiling data from cancer patients' disease, in an effort to **reduce time-to-treatment for patients**, while learning of potentially **novel therapeutic regimens**, to address these two unmet needs for cancer patients; both of which lend to reducing the projections of cancer deaths. MDCI will accomplish this by looking at a patient's tumor specimen by validated clinical immunohistochemistry(IHC) assays coupled with whole exome and whole transcriptome sequencing. Based on IHC data, as well as previous medical history, all potential clinical trial options are returned; reducing time-to-treatment by supporting screening against all trial options, instead of one at a time. Sequencing data collected will allow researchers to correlate to outcome, potentially discovering novel targets/pathways, as well as co-expression of biomarkers; allowing for data-driven, novel treatment regimens.

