This is a multicenter study, enrolling participants with advanced/metastatic disease for the purpose of biospecimen collection (tumor tissue and blood samples) for broad molecular profiling and examining the expression of specific antigens (e.g. NY-ESO-1, LAGE-1a), immune markers (e.g. PD-L1), tumor immune infiltrates, differentially expressed genes, and Human Leukocyte Antigen (HLA) genotype. Results from validated clinical assays will support the referral of eligible participants into an appropriate GSK Clinical trial. These results, paired with clinical & sequencing results, will facilitate the building of a scientific database (GSK Clinical Science Database) permitting investigation of mechanisms underpinning the activity of targeted agents, resistance to therapy, and conducting other correlative analyses.

- Participants who are HLA-A*02:01, HLA-A*02:05, HLA-A*02:06 positive and whose tumor tissue expresses NY-ESO-1 and/or LAGE-1a by a validated assay (based on relevant clinical cut-off detailed in SRM & other inclusion/exclusion criteria) may be referred to GSK3377794, GSK3845097, &/or GSK3901961 clinical trial(s)
- Participants whose tumor tissue is positive by validated PDL-1 (SP263) IHC (based on relevant clinical cut-off detailed in SRM & other inclusion/exclusion criteria) may be referred to GSK3359609 clinical trial(s).
- Based on BRCA 1 or 2 mutation, Homologous Recombination Deficiency (HRD) &/or PDL-1(SP263) tumor status, participants may be referred to Niraparib trial(s).

Validated clinical biomarker data will be returned to the physician, as well as a subset to the participant, through individual portal systems. This study will also utilize tumor and blood samples for research purposes, including potential biomarker, companion diagnostic, and investigational genetic research.

It is anticipated that this molecular disease characterization protocol will support screening for GSK Oncology trials, outlined within SRM.

Disclosure Statement: This is a single arm interventional molecular analysis study with no administration of investigational product and no masking.

Number of Participants: Approximately 400 participants will be enrolled into this molecular analysis study.

Study Groups and Duration:

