4. STUDY DESIGN

4.1. Overall Design

This is a multicenter study, enrolling patients with advanced/metastatic disease for the purpose of collecting tumor tissue and blood samples for broad molecular analysis and examining the expression of specific biomarkers using validated clinical assays. The study involves three primary visits (Figure 1).

Figure 1 Study Schema

Footnotes: ¹MDCI will be an optional protocol under select GSK oncology protocols; ²In the case that Visit 1 and 2 are combined, all corresponding samples must be collected per the SoA (Section 1.3 Table 1) at this visit and after eligibility is confirmed; ³Subset of data to be shared on Gather Share Know; ⁴Patient's molecular profile and medical history will be compared against the eligibility criteria of select GSK oncology protocols to identify potential trial options; ⁵Visit 3 may occur remotely via telehealth/phone visit (optional).

At **Visit 1**, informed consent will be obtained from participants to enroll in the study, specifically to undergo a multiplex biomarker characterization, and to store and share a subset of their data through a Participant Hub (Gather Share Know). Registering for Gather Share Know is optional; a standardized template will be created and included as an annexure to the regular ICF.

Upon consenting to participate in the MDCI screening process, the participant will continue with assessments per schedule of activities (SoA Table 1). For most participants, the expected duration between V1 and V3 is ≤ 8 weeks; which is dependent on the receipt and the type of tumor biopsy sample submitted.

During **Visit 2**, a tumor specimen will be collected or submitted, as per tumor specimen collection requirements (refer to SRM and Study Laboratory Manual). The specimen will be evaluated by IHC to determine the expression of tumor specific antigens and immune markers such as, but not limited to, NY-ESO-1 and PD-L1. A portion of the tumor specimen will also be analysed by whole exome sequencing (WES), as well as whole transcriptome sequencing (WTS) to determine patients' molecular profile; these sequencing data will not be used for trial referral.

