9.1.6. Dissemination of Clinical Study Data

- Where required by applicable regulatory requirements, an investigator signatory will be identified for the approval of the clinical study report. The Investigator will be provided reasonable access to statistical tables, figures, and relevant reports and will have the opportunity to review the complete study results at a GSK site or other mutually-agreeable location.
- GSK will also provide the Investigator with the standard report of the tumor biopsy results, and applicable clinical trials, from DNAseq and RNAseq analysis initially performed on tumor biopsy.
- GSK will also provide a subset of CLIA-validated results back to participants through Gather Share Know Participant Hub. List of results that will be shared can be found in SRM.
- The procedures and timing for public disclosure of the protocol and results summary and for development of a manuscript for publication for this study will be in accordance with GSK Policy.
- GSK intends to make anonymized participant-level data from this trial available
 to external researchers for scientific analyses or to conduct further research that
 can help advance medical science or improve patient care. This helps ensure the
 data provided by trial participants are used to maximum effect in the creation of
 knowledge and understanding.
- A manuscript will be progressed for publication in the scientific literature if the results provide important scientific or medical knowledge.

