4.2.2. Main analytical approach

"Enrolled" analysis set will be used to perform primary endpoint analysis.

A summary table containing biomarker status of participants will be provided. Biomarker status includes Inducible T-cell Co-Stimulator (ICOS) status, New York esophageal squamous cell carcinoma 1 (NY-ESO-1)/Cancer testis antigen 2 (LAGE-1a) status and Programmed death protein 1 Ligand (PD-L1) status.

This summary table contains number and percentage of participants with positive/negative status by biomarker (ICOS, NY-ESO-1/LAGE-1a and PD-L1).

A subject level listing containing biomarker status of participants will also be provided.

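### Protocol 4.1 bars tumor sequencing from trial referral while 9.1.6 returns trial matches from it; separately, the SAP's primary table omits three named referral markers (BRCA 1/2, HRD, HLA-A*02)

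*Protocol*

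**What the plan says.** **Referral basis.** Protocol 4.1 states that part of the tumor specimen "will also be analysed by whole exome sequencing (WES), as well as whole transcriptome sequencing (WTS") and adds that "these sequencing data will not be used for trial referral". Several places fit that rule. The rationale in the synopsis (1.1) reads "Based on IHC data, as well as previous medical history, all potential clinical trial options are returned". The overall design in the synopsis rests referral on validated clinical assays, and 4.1 describes the Physician Portal's trial list in the same way.

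Protocol 9.1.6 differs. It promises the investigator a standard report of the tumor biopsy results together with "applicable clinical trials, from DNAseq and RNAseq analysis initially performed on tumor biopsy". Section 4.1 also has physicians go through results with participants at Visit 3 and refer them for further screening where the results suggest eligibility for a trial.

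**Markers.** The synopsis gives three referral routes:
- the T-cell receptor trials, on HLA-A*02:01, 02:05 or 02:06 together with NY-ESO-1 and/or LAGE-1a;
- the GSK3359609 trials, on PD-L1 (SP263);
- niraparib trials: "Based on BRCA 1 or 2 mutation, Homologous Recombination Deficiency (HRD) &/or PDL-1(SP263) tumor status, participants may be referred to Niraparib trial(s").

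The primary endpoint (Protocol 1.1; SAP 4.2.1) is the profile of selection biomarkers for the sponsor's oncology pipeline, with further markers left to the study reference manual. Protocol 8.4 says that key markers, including those considered for patient selection, will be tabulated. SAP 4.2.2 then specifies: "This summary table contains number and percentage of participants with positive/negative status by biomarker (ICOS, NY-ESO-1/LAGE-1a and PD-L1"). SAP 4.7 declares no departure from the analyses in protocol amendment 3.

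**The concern.** These are two separate inconsistencies.

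The first concerns what a site may do with a sequencing report. Section 4.1 excludes tumor exome and transcriptome data from referral. A site that receives the 9.1.6 report and follows the Visit 3 instruction could refer on exactly those data. The protocol's answer to false positive and false negative results (risk table, 2.3.1) is that assays used to determine trial eligibility have acceptable predictive values. The text does not show that this assurance covers data which 4.1 excludes from referral. Protocol 8.4.2 also plans counts of participants referred, by tumor type and treatment trial. Those counts are hard to interpret if the basis for referral is not fixed.

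The second concerns the completeness of the primary summary. The study exists to describe patient-selection markers. If markers that the protocol itself names for referral have no row in the primary table, and the SAP reports no change, a reader of the study report cannot tell whether they were left out deliberately or by oversight.

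**Working it through.** No arithmetic beyond a count applies. The study tests no hypothesis (Protocol 8.1; SAP 2), and the expected 400 participants has no statistical derivation to reproduce (Protocol 8.2). The check sets the passages side by side.

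**Step 1: are 4.1 and 9.1.6 about the same data?** In 4.1 the excluded data are exome and transcriptome sequencing of the tumor specimen. In 9.1.6 the report comes from DNA and RNA sequencing of the tumor biopsy. The material and the kind of data match. One passage excludes them from referral; the other derives applicable trials from them.

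**Step 2: does another passage resolve it?**
- The validated-assay wording in 4.1 describes the Physician Portal's list. It does not limit the 9.1.6 report.
- In 9.1.6 the CLIA-validated qualifier is attached to results returned to participants, not to the investigator's report.
- No passage marks the trials in the 9.1.6 report as information only.
- A schema footnote says that the patient's "molecular profile and medical history will be compared against the eligibility criteria of select GSK oncology protocols to identify potential trial options". Section 4.1 uses sequencing to determine the molecular profile, but its database list counts both IHC and sequencing as molecular profiling. The footnote can be read either way, and I do not rely on it.

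The conflict between 4.1 and 9.1.6 is therefore unresolved in the text.

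**Step 3: which referral markers have a row in the primary table?**

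| Marker named for referral (Protocol 1.1) | Route | Row in SAP 4.2.2 table |
|---|---|---|
| HLA-A*02:01, 02:05, 02:06 | T-cell receptor trials | No |
| NY-ESO-1/LAGE-1a | T-cell receptor trials | Yes |
| PD-L1 (SP263) | GSK3359609; niraparib | Yes |
| BRCA 1/2 mutation | Niraparib | No |
| HRD | Niraparib | No |

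Counting the HLA alleles as one marker and NY-ESO-1/LAGE-1a as one, five markers are named and two have rows: 5 − 2 = 3 without. On the niraparib route alone, one of three markers (PD-L1) has a row.

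**Step 4: is the assay behind BRCA and HRD stated?** The synopsis names an assay (SP263) for PD-L1 only. The available text gives no source for BRCA or HRD status.

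**The case against.** **On referral.** The protocol states its basis several times and mostly consistently: IHC with medical history, validated clinical assays, and an explicit exclusion of tumor sequencing. Section 9.1.6 is one bullet in an appendix on dissemination, does not use the word referral, and may be loosely worded. Referral leads only to further screening, so a match does not by itself enrol or treat anyone. This stands in part. It would be too strong to say that the design has no referral rule. But the bullet is operative text, it describes a report that the investigator will hold, and nothing subordinates it to 4.1.

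**On BRCA/HRD.** A reader might infer that referral on BRCA or HRD directly contradicts the exclusion in 4.1. The documents do not support that. It would follow only if BRCA/HRD status came from the tumor exome or transcriptome data, and no available passage says so. A separate validated assay could supply it, and assay detail is deferred to the study reference manual or may lie in Protocol Sections 7.6 and 7.7, which are not in the public text. What remains is an unstated source.

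**On the primary table.** The endpoint is worded generically and points to the study reference manual. The SAP covers a synoptic report, and its numbering runs from 4.3 to 4.5 in the public text, so other analyses may exist. Protocol 8.4.2 separately plans a summary of HLA-A subtypes and of in vitro diagnostic assay results. A deliberately short primary table is therefore possible. That is a fair reason to let the sponsor record the choice instead of insisting on rows. It does not explain why markers that the protocol names for selection are absent while SAP 4.7 reports no change.

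Two further inferences fail. The niraparib route is not wholly missing from the table: its markers are joined by and/or, and PD-L1 has a row. Nor is the marker set self-contradictory. It is incomplete, and this does not follow from the sequencing sentence in 4.1.

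**Conclusion.** Both inconsistencies hold, as separate points.

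1. Protocol 4.1 and 9.1.6 conflict on whether tumor sequencing may produce trial matches that a physician then acts on. The passages must be reconciled; which basis is right is for the sponsor to state. No contradiction is shown for BRCA/HRD, only that the available text does not give the assay source.
2. The primary biomarker table in SAP 4.2.2 lacks three of the five referral markers named in the synopsis (BRCA 1/2, HRD and HLA-A*02), and SAP 4.7 does not record the omission.

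The consequence is limited to clarity for sites, the meaning of the referral counts, and the completeness of the primary summary. Alpha, power and sample size are untouched. The number of participants affected is not given and cannot be derived. The conclusion assumes that unseen material, namely the study reference manual, Protocol 7.6 and 7.7 and any SAP 4.4, does not already settle these points. Even if it did, the wording of 4.1 and 9.1.6 would still need aligning.

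**What to change.** - **Protocol 4.1 and 9.1.6:** replace the conflicting text with one statement of which assay results may generate a trial match. The sponsor chooses the basis. Check that the synopsis, the portal description and the investigator report template follow it.
- **BRCA/HRD:** state which assay supplies each result, or cite the section of the study reference manual that does.
- **SAP 4.2.2:** add rows for BRCA 1/2, HRD and HLA-A*02, each with the number tested, the number and percentage positive, and the assay source. If the sponsor prefers to keep the shorter table, record the omission and its reason in SAP 4.7. The PD-L1 row already exists and needs no change.

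The cost is a wording alignment, a check of one report template, and three further table rows or one SAP entry. No new sample or assessment is requested.

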4.2. End of Study Definition

A participant will be determined to have completed the study for the primary objectives if:

- The participant signed consent to participate on one of the GSK treatment protocols
- After two years of longitudinal follow-up (Table 2)

The protocol will remain open until all designated GSK-sponsored clinical trials are closed to enrolment and the last participant in this study has completed their last visit or until a date otherwise determined at the discretion of GSK.

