Tumor Specimen ⁽³⁾		Х	1. Subsequent treatment and the associated clinical outcomes of interest will be collected for participants who do not enroll in a treatment protocol.	
Tumor Imaging	X ⁽⁴⁾	X (5)	Survival follow up will be conducted for participants who do not enroll in a treatment protocol.	
Vitals ⁽⁶⁾	Х	Х		
Review of AEs and SAEs that are related to study procedure(s) or lead to study withdrawal	Х	Х	3. If patient progresses while on Standard of Care (SoC), a tumor biopsy may be taken for re-analysis & potential referral to a treatment trial based on results. Image guidance preferred when feasible. Images from guidance procedure will be collected (see Section 7.2.3).	
Current anti-cancer therapies(1)	Х	Χ	4. Any imaging for standard of care tumor assessment by CT, MRI, PET, nuclear medicine,	
Survival Follow up ⁽²⁾	Х	Х	Xray, or photography that was conducted will be collected. Visit window for imaging ±8 weeks.	
			5. Imaging for tumor assessment conducted within 4 weeks prior to biopsy will be collected. Imaging conducted after biopsy is not required to be collected.	
			6. Blood Pressure, Pulse Rate and Temperature	

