A liquid biopsy (blood) will also be taken at Visit 2 to analyse circulating tumor DNA (ctDNA), and/or exosomes. In addition, participants will also provide mandatory blood samples for biomarker, validated clinical biomarker testing, and genetic research, as well as tumor imaging with CT/MRI. *HLA* genotype will be determined from whole blood DNA tested at a central laboratory.

CCI

WES data from the blood will also be used in conjunction with the SNP genotyping data to assess the effect of host genetic variation in one or more candidate genes or across the genome on cancer risk, progression, and response to cancer treatments. Details of testing and management of all samples can be found in the respective sections of the SRM and Study Laboratory Manual.

A subset of the generated results will be uploaded to the Physician Portal for review, followed by the Gather Share Know Participant Hub. Physicians will review the results with participants at Visit 3. If the results indicate eligibility for a specific clinical trial, appropriate referrals to those trials will be made by physician for further screening. Participants will only be provided access to their selected results through the Gather Share Know Participant Hub after they have received information on the significance/benefits of the testing. Training will be provided to all participants who consent on how to access and navigate the hub.

All participants will undergo a follow-up safety assessment for any serious adverse events (SAEs) assessed as related to protocol-mandated study procedures or leading to study withdrawal.

The study protocol will remain open until all designated GSK-sponsored impacted clinical trials (outlined in SRM) are closed to enrolment & all participants have completed this study or at the discretion of GSK.

Participants ineligible for Clinical trials

If a patient does not enroll onto a GSK study, or any other investigational study, , and who procced to receive Standard of Care (SoC) therapy, disease will continue to be monitored under MDCI following a separate Schedule of Activities (SoA) for longitudinal follow-up (Table 2). Accordingly, physicians will be asked to enter/ report all anticancer therapies received and the participant's survival status during follow-up, in order to characterize treatment patterns and survival outcomes respectively.

The following portals will be used for this study:

1. Gather Share Know Participant Hub

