7.1. Gather Share Know Participant Hub

The 'Gather Share Know' Participant Hub is an optional, web-based application with a patient facing solution will provide the following capability:

• A guide/overview of Gather Share Know platform: information provided, how to use and potential benefits.

- Patient Credentials: Following completion of informed consent, patients will be provided credentials to log into the Gather Share Know Participant Hub.
- Information about the Study: Study Site and PI information and study progress (e.g. enrolled, assessments, available results, study complete, etc.).
- Study Visits: List of visits and what to expect for each visit.
- Embedded and / or linked educational materials from credible sources (e.g. National Cancer Institute) with information specific to patient's diagnosis: This will be provided by GSK to participant hub vendor to populate based on diagnosis.
- Laboratory results (e.g. validated clinical biomarker data) in simple, easily
 understood, language: Results will come from the lab vendor conducting the
 analysis. Following agreed physician review period, this data will be published to
 participant hub.
- Trial Matching: The participant hub can recommend GSK Oncology trials that
 patients might be eligible for based on the MDCI lab and biomarker results and a
 subset of inclusion / exclusion criteria. Information about these trials and study PI
 or staff contacts will be provided to allow patients to follow up to express interest.
 These patients can also be notified as new GSK Oncology trials become available
 where they may be eligible.

List of GSK trials to use for matching and associated enrolment timings will be provided by GSK and updated accordingly over time. Rules for trial matching based on biomarker results and a subset of inclusion / exclusion criteria will be provided. Biomarker results will come from lab vendor. Data to assess against subset of inclusion / exclusion criteria will come from InForm eCRF and where applicable, further information from the study site personnel. An outline of what data will be returned to patients, as well as directives & resources for counselling, can be found in the SRM.

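### Protocol 4.2 completes a participant at signed consent to a GSK treatment protocol, while follow-up under 4.1 and Table 2 turns on enrolment, so those who sign but fail screening have conflicting status

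*Protocol*

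**What the plan says.** Section 4.2, under the end-of-study heading, opens its participant-level rule with "A participant will be determined to have completed the study for the primary objectives if" and lists two conditions. The first is "The participant signed consent to participate on one of the GSK treatment protocols". The second is two years of follow-up on Table 2. They can only be alternatives, because a participant who moves into a treatment trial does not go through Table 2.

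Section 4.1 sets the follow-up rule. It begins "If a patient does not enroll onto a GSK study, or any other investigational study", adds that the patient goes on to standard of care, and then places the patient on the Table 2 schedule. A Table 2 footnote uses the same trigger: "Survival follow up will be conducted for participants who do not enroll in a treatment protocol".

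Referral comes before the treatment trial's own eligibility work. Section 4.1 says "appropriate referrals to those trials will be made by physician for further screening". Section 7.1, on the participant hub, says "Rules for trial matching based on biomarker results and a subset of inclusion / exclusion criteria will be provided".

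**The concern.** Consent to a treatment trial and enrolment in it are separate events, with that trial's screening in between. Section 4.2 uses the first event and the follow-up rules use the second. For a participant who signs and then fails screening, two sites could act in opposite ways and each cite the protocol.

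What is at stake is the longitudinal data. Section 8.4.2 defines time to next treatment, time to progression and overall survival, each measured from the start of an anticancer therapy. Standard therapy that begins after the failed screening would begin after a 4.2 closure, so MDCI would not follow its course. The synopsis ties referral to validated marker results, so those who sign are likely to be enriched for the selection markers. Section 8.4 plans to relate molecular profiles to phenotypes such as treatment outcome. Loss of follow-up that depends on the site's reading, and probably on marker status, would weaken that comparison. The SAP's disposition summary (6.1.1) also reports subject status, which needs one completion rule.

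**Working it through.** The plan states no figure on this point, and no power or sample-size formula applies: Protocol 8.1 tests no hypothesis, and 8.2 gives 400 as an expectation without a derivation. The check is a comparison of the rules for one case.

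**Case.** A participant reaches Visit 3, signs consent for a GSK treatment protocol, fails that protocol's screening, receives standard of care and enters no other trial. Sections 4.1 and 7.1 make this possible, since matching uses only part of the eligibility criteria and referral leads to further screening.

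| Place in protocol | Rule turns on | Result for this participant |
|---|---|---|
| 4.2, first condition | Signed consent | Complete |
| 1.1 Synopsis, study groups | Enrolment in a GSK trial | Not in group (a); falls to longitudinal group (b) |
| 1.1 Synopsis, follow-up sentence | Non-enrolment in any trial | May stay on Table 2 |
| 4.1 | Non-enrolment in any trial, plus standard of care | Followed on Table 2 |
| Table 2 note | Not eligible for a trial, plus standard of care | Followed on Table 2 |
| Table 2 footnote 2 | Non-enrolment in a treatment protocol | Survival follow-up |
| 8.3, Ineligible for Treatment Trial | Non-enrolment in a GSK treatment study | In this population |

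**Does any passage rank the rules?** No. Section 5.3 allows consent to another intended treatment protocol after discussion with the sponsor, but does not say whether the first consent has already completed the participant, or whether a completed participant can return to Table 2.

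**What one closure costs.** Table 2 runs every 26 weeks to week 104: 104 / 26 = 4 scheduled visits with liquid biopsy and survival follow-up, plus the progression visit with possible re-biopsy.

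**How many.** Number who sign and fail = 400 × (proportion who sign) × (proportion of signers who fail screening). The documents give neither proportion. By assumption only:

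- 5% sign and 10% of those fail: 400 × 0.05 × 0.10 = 2
- 15% sign and 20% fail: 400 × 0.15 × 0.20 = 12
- 25% sign and 40% fail: 400 × 0.25 × 0.40 = 40
- 30% sign and 50% fail: 400 × 0.30 × 0.50 = 60

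The spread from 2 to 60 shows that the count is not known. Each figure is also an upper bound for its assumptions, because some who fail will enter another trial and so fall outside the 4.1 follow-up rule.

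**The case against.** The strongest reply is that 4.2 limits itself to completion for the primary objectives. The primary objective is the molecular and immunological profile, from samples taken at Visit 2, before any referral. On that reading a participant can be complete for the primary objective and still be followed, and 4.2 never says that follow-up ends. This has weight, and it means that 4.2 need not be read as closure. It does not remove the ambiguity: the rule sits under the end-of-study heading, its other condition is the end of Table 2 follow-up, and the protocol has no other participant-level completion rule.

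The consent trigger was also deliberate. The Amendment 01 history gives documented evidence of completion as its reason. That explains the choice but does not reconcile it with the enrolment-based rules.

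Two further points stand. Most of the loss of marker-positive participants from the longitudinal group is by design, since those who enrol in a treatment trial leave it; the conflict adds only those who sign and fail. And the visible SAP plans no time-to-event output, so the consequence falls on the descriptive analyses in Protocol 8.4.2 and on the scientific database.

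A reader might infer that these participants are followed under no rule at all. The documents do not support that: 4.1, the Table 2 note and footnote 2 all cover the case above. The rules overlap and conflict; they leave no gap. Nor does 4.1 follow everyone who does not enrol, since it also requires standard of care and no other investigational study, and the synopsis wording is only permissive.

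**Conclusion.** The inconsistency is real and should be corrected, but it is limited. It concerns participants who sign a GSK treatment consent, are not enrolled, and receive standard of care outside any trial. They are complete under 4.2 and due for follow-up under 4.1 and Table 2, with nothing to say which prevails.

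Follow-up is lost only where a site takes 4.2 as closure. Enrichment of this group for selection markers is an inference from the referral rules, not a documented fact. One might also infer that such participants are common, or that a particular tumor type would lose most of its marker-positive patients; without consent rates, screen-failure rates or counts by tumor type, neither can be claimed. The SAP's primary summary of biomarker status in the Enrolled set (4.2.2) is unaffected.

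**What to change.** Reconcile 4.2 with 4.1, Table 2 and 8.3:

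- In 4.2, base the first completion condition on enrolment in a GSK treatment protocol rather than on signed consent.
- In 4.1 and Table 2, state that a participant who signs a treatment-protocol consent but is not enrolled, and who meets the existing 4.1 conditions (standard of care, no other investigational study), continues on Table 2. Bring the Table 2 note and the permissive synopsis sentence into line.
- Add an eCRF field for the outcome of treatment-trial screening. This also keeps the documented evidence of completion that Amendment 01 sought.

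The text changes are a few sentences, and no new visit schedule or timing anchor is needed. The costs are a protocol amendment with ethics approval (9.1.1), one eCRF field, and existing Table 2 follow-up for participants whom some sites would otherwise have closed. That number is unknown but is limited to those who sign and are not enrolled.
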